6. ANALYSIS POPULATIONS

6.1. Efficacy Populations

The intent-to-treat (ITT) population is defined as all patients randomly assigned to study treatment and is based on randomized treatment assignment regardless of whether or not treatment was administered. Unless otherwise specified, all efficacy analyses will use the ITT population.

6.2. Safety Population

The safety population is defined as all randomized patients who receive at least 1 dose or partial dose of study drug (enzalutamide or placebo). Unless otherwise specified, all safety analyses will use the safety population according to the actual treatment received (not the treatment assigned).

7. DEFINITIONS, COMPUTATIONS, AND CONVENTIONS

7.1. Definitions and Computations

Study Day

Study day will be calculated in reference to the date of randomization (Study Day 1). For assessments conducted on or after the randomization date, study day is calculated as (assessment date – randomization date + 1). For assessments conducted before the randomization date, study day is calculated as (assessment date – randomization date). There will be no Study Day 0.

Date of First Dose and Date of Last Dose of Study Drug

The date of the first dose of study drug is defined as the date a patient receives the first dose of study drug (enzalutamide or placebo). The date of the last dose of study drug is defined as the date a patient receives the last dose of study drug (enzalutamide or placebo).

Treatment Day

Treatment day will be calculated in reference to the date of the first dose of study drug. Treatment Day 1 corresponds to the date a patient receives the first dose of study drug. For assessments conducted on or after the date of the first dose of study drug, treatment day will be calculated as (assessment date – date of first dose of study drug + 1). There will be no Treatment Day 0.

Treatment Period

The treatment period is defined as the period of time from the date and time of the first dose of study drug through the date of last dose.

Treatment-Emergent Period

The treatment-emergent period is defined as the period of time from the date and time of the first dose of study drug through the date of last dose + 30 days (or the day before initiation of a new antineoplastic treatment, whichever occurs first).

Treatment Duration

Treatment duration is defined as the duration of time from the date of the first dose of study drug to the date of the last dose of study drug as follows:

Treatment Duration (days) = Date of last dose of study drug – Date of first dose of study drug + 1.

Treatment Duration (months) = (Date of last dose of study drug – Date of first dose of study drug + 1)/30.4375.

Long-Term Follow-up Period

The long-term follow-up period will start the day after the last day of study drug treatment and will continue through the data cutoff date.

Baseline Value and Postbaseline Value

Unless otherwise specified, the baseline value is defined as the last measurement before the first administration (date and time) of study drug. If time is not available, then date only will be used. Postbaseline value is defined as a measurement taken after the first administration of study drug. Change from baseline is defined as (postbaseline value – baseline value). For laboratory assessments and vital signs, only date and time of study drug administration and measurement will be considered when calculating baseline value. If time is not available, then date only will be used.

New Antineoplastic Therapy, Cytotoxic Chemotherapy and Bone-Targeting Agent Classification

All treatment modalities study participants receive during the study are collected via the Concomitant Medications CRF page. As these classifications for concomitant medications are critical for study results, the study medical monitor will independently review each concomitant medication and determine whether they belong to one of these categories. The classification process will only consider the medication name (by preferred term), and will be performed blinded to treatment. The study medical monitor will sign the completed list of classifications, and the list will be documented in the study folder. No changes to this classification will be allowed after study unblinding.

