5.3. Permanent Treatment Discontinuation

Permanent treatment discontinuation is defined as cessation of study drug administration. Safety follow-up ([Section 5.4.1](#)) and long-term follow-up ([Section 5.4.2](#)) will still be performed.

Temporary treatment interruption due to an adverse event is not considered permanent discontinuation. Patients whose treatment is interrupted due to an adverse event and restarted will continue to have regularly scheduled study visits based on their randomization date.

The primary reasons for permanent treatment discontinuation are listed in [Table 5](#). Cross-references are provided to protocol sections with additional information.

Table 5. Primary Reasons for Permanent Treatment Discontinuation

Reason	Comment
Adverse event or intercurrent illness	Any intolerable adverse event that cannot be ameliorated by the use of adequate medical intervention or that in the opinion of the investigator or medical monitor would lead to undue risk if study treatment were continued. Refer to Section 8 .
Gross noncompliance with protocol (violation)	The medical monitor or investigator may request permanent discontinuation of study drug treatment in the event of a major protocol deviation, lack of cooperation, or noncompliance.
Disease progression	Study drug treatment will be discontinued after development of radiographic progression if the investigator considers continuing study drug not to be beneficial. Initiation of new therapy for prostate cancer (with the exception of cytotoxic chemotherapy, androgen receptor inhibitors, and investigational agents) at the time of radiographic progression will not mandate discontinuation of study drug if the investigator considers continuing study drug to be beneficial.
Laboratory abnormality defined by protocol	
Creatinine >354 µmol/L (4.0 mg/dL)	
AST, ALT, or total bilirubin >5 times the upper limit of normal (ULN) AST or ALT > 3 times ULN and total bilirubin > 2 times ULN without findings of cholestasis	
Absolute neutrophil count ≤750/µL	
Platelet count <50,000/µL	
Seizure	Regardless of resolution of any identified etiology. Refer to Section 1.4 .
Death	Refer to Section 1.1 .
Loss to follow-up	Refer to Section 5.5 .
Sponsor discontinuation of study	The sponsor reserves the right to terminate the study anytime as described in Section 13.6 . The sponsor will terminate this study following completion of the study objectives, or earlier if deemed necessary.

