8.1.4. Time Period for Collecting AE/SAE Information

The time period for actively eliciting and collecting AEs and SAEs (“active collection period”) for each subject begins from the time the subject provides informed consent, which is obtained before the subject’s participation in the study (ie, before undergoing any study-related procedure and/or receiving investigational product), through and including a minimum of 30 calendar days; except as indicated below after the last administration of the investigational product.

If a patient begins a new anticancer therapy, the recording period for all AEs ends at the time the new treatment is started. However, the reporting of SAEs should continue beyond this period if the investigator believes there to be at least a reasonable possibility of the SAE being related to investigational product. Phone patients for follow up if they do not come to the clinic within the follow up period.

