10.4. Safety Analyses

All safety analyses will use the safety population.

Safety analyses will be summarized by treatment. The treatment-emergent period is defined as the period of time from the first dose date of study drug to approximately 30 days after the last dose of study drug or the date of initiation of a new antineoplastic treatment, whichever occurs first.

Adverse events occurring during the adverse event reporting period will be coded according to the Medical Dictionary for Regulatory Activities (MedDRA) and tabulated by system organ class and by preferred term within each system organ class. Tabular summaries will include the incidence overall (number and percentage of patients with treatment-emergent adverse events classified by system organ class and preferred term); incidence by intensity (severity graded according to the CTCAE, version 4), causality, seriousness, and outcome (eg, leading to discontinuation of study drug); and other presentations as appropriate.

Serious adverse events occurring prior to study treatment will be tabulated separately if considered related to study procedure.

Patients with the same adverse event reported more than once will be counted once at the maximum severity or strongest relationship to study drug.

Toxicity for laboratory parameters (hematology, serum chemistry) will be graded using the CTCAE, version 4. Shift tables will be provided as appropriate for each parameter to summarize baseline toxicity grade versus postbaseline toxicity grade. For each laboratory parameter that is not gradable by the CTCAE, a shift table based on the normal range (low, normal, and high) will be provided to summarize baseline result versus postbaseline result. For each laboratory parameter, the baseline laboratory value is defined as the last laboratory value collected on or prior to the date of the first dose of study drug.

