5. Must be within 42 days before randomization. Screening includes posteroanterior and lateral chest x-ray or chest CT scan, whole-body radionuclide bone scan, and abdominopelvic CT/MRI. If the screening bone scan shows a lesion suggestive of metastatic disease, the patient will be eligible only if a second imaging modality (plain film, CT, or MRI) excludes bone metastasis. If the imaging results are equivocal or consistent with metastasis, the patient is not eligible for enrollment. Use the same imaging method throughout the study.
6. Perform approximately every 16 weeks, but obtain images sooner if progression is clinically suspected. Radiographic imaging should be performed until radiographic progression is identified and confirmed by independent central radiology review per protocol. A second imaging modality (plain film, CT, or MRI) confirmation of bone progression is required when bone lesions are found in a single region on the bone scan.
7. If disease progression is suspected, perform imaging studies as appropriate.
8. Complete, sign, and fax the randomization authorization form to the medical monitor at the number provided on the form at least 2 business days before the day 1 visit.
9. Assess systems per standard of care at the study site and as clinically indicated by symptoms. Includes assessment of vital signs and weight (height only at screening).
10. Symptom directed and includes investigating any new abnormalities and assessment of vital signs.
11. Questionnaires will be completed for patients who come to the clinic.
12. Collect nonserious adverse event information from the time of first dose of study drug through safety follow-up. If no safety follow-up, collect adverse event information through 30 days after the last dose of study drug. Phone patients for follow-up if they do not come to the clinic.
13. May obtain at clinic visits, by phone contact, chart review, etc. Includes survival status, new antineoplastic therapies for prostate cancer, opiate use, skeletal-related events, and interventions due to locoregional progression.
14. Refer to the laboratory instruction manual for sample processing.

Study Period or Visit	Screening	Treatment			Unscheduled	Safety FU	Long-Term FU
Study Week	-4 to -1	1	5	17 Then Every 16	Varies [1]	Varies [2]	Every 16
Study Day	-28 to -1	1	29	113	na	na	na
Window (Days) [3]	na	na	±5	±5	na	±7	±7

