- Sponsor discontinuation of study: The sponsor has the right to terminate the study anytime. However, the sponsor will ensure that enzalutamide will be available to all patients who participate in the open-label period for as long as they are deriving clinical benefit.

Patients who discontinue treatment with enzalutamide for any reason will have safety follow-up approximately 30 days after the last dose or before initiating treatment with a cytotoxic chemotherapy or investigational agent for prostate cancer. If a new cytotoxic or investigational anticancer treatment is initiated before 30 days after the last dose of enzalutamide, then safety follow-up should occur immediately before starting the new treatment. Long-term follow-up will commence after completion of safety follow-up.

Loss to follow-up: Every reasonable effort should be made to contact patients apparently lost to follow-up to complete study-related assessments, record outstanding data, and retrieve study drug. Following unsuccessful telephone contact, an effort to contact the patient by mail using a method that provides proof of receipt should be attempted. Alternate contacts are permissible if the patient is not reachable (eg, primary care providers, referring physician, relatives). Such efforts should be documented in the patient's source documents.

Prior and Concomitant Medications:

Medications taken within 4 weeks before open-label day 1 and any medications prescribed for chronic or intermittent use, or dose adjustments of these medications, must be recorded on the case report forms and source documents.

Concomitant medications include all vitamins, herbal remedies, and over-the-counter and prescription medications. Concomitant medications will be assessed at screening and all clinic visits. If the use of any medication during the study is due to an adverse event, the adverse event must be recorded on the adverse event case report form and in the patient's clinical record.

Ongoing androgen deprivation therapy with a GnRH agonist/antagonist to maintain castrate levels of testosterone is required throughout the study if the patient has not had a prior bilateral orchiectomy.

The use of concurrent cytotoxic chemotherapy or investigational anticancer agents is prohibited.

Initiation of bisphosphonates or denosumab for bone health is allowed. Standard of care supplementation with calcium and vitamin D is encouraged.

Statistical Methods:

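### The treatment-emergent period ends when a new antineoplastic therapy starts, even for patients whom the protocol lets stay on study drug

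*SAP*

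**What the plan says.** **The analysis window.** SAP 7.1 runs the treatment-emergent period from first dose to 30 days after last dose, "or the day before initiation of a new antineoplastic treatment, whichever occurs first". Protocol 10.4 stops it about 30 days after last dose "or the date of initiation of a new antineoplastic treatment, whichever occurs first". The two differ by one day at the cut-off, and neither makes it conditional on study drug having stopped.

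**What uses the window.** Treatment-emergent adverse events (SAP 9.8.1), laboratory summaries (SAP 9.8.2) and vital-sign summaries (SAP 9.8.3) are all confined to it. Treatment duration (SAP 7.1 and 9.5) is not: it runs from first dose to last dose.

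**Study drug alongside new therapy.** Protocol 5.3, Table 5, says that starting a new prostate cancer therapy at radiographic progression "will not mandate discontinuation of study drug if the investigator considers continuing study drug to be beneficial". Protocol 3.1 and 5.2.3 agree. All three except cytotoxic chemotherapy, androgen receptor inhibitors and investigational agents, and Protocol 7.2 makes those three classes grounds for permanent discontinuation. For the open-label period, Supplement 1 says: "The use of concurrent cytotoxic chemotherapy or investigational anticancer agents is prohibited".

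**Collection at the site.** Protocol 8.1.4: "If a patient begins a new anticancer therapy, the recording period for all AEs ends at the time the new treatment is started". Protocol 8.1.4.1 adds that serious events after the collection period are reported if the investigator learns of them, with possibly related ones as the minimum. Table 4 asks for new and ongoing adverse events at each on-treatment visit. Appendix 5, note 12: "Collect nonserious adverse event information from the time of first dose of study drug through safety follow-up". Note 13 of Supplement Table 1 also runs through safety follow-up and names no stop at new therapy.

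**The concern.** A cut-off at new therapy makes sense when the new therapy follows the end of study drug: it keeps the next treatment's toxicity out of the 30-day tail. Here the two may be given together. A patient who adds a permitted agent at progression and stays on study drug is still exposed and still adds to treatment duration, but nothing that starts after that date is treatment-emergent.

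The main adverse-event displays are numbers and percentages of the whole safety population (SAP 7.2 and 9.8.1). Such a patient therefore stays in the denominator while his later events leave the numerator. The outputs can also disagree with each other. If an adverse event stops study drug after the added therapy, it counts as a reason for discontinuation in the disposition summary (SAP 9.1) but not in the table of treatment-emergent events leading to discontinuation (SAP 9.8.1). No supplementary on-treatment summary is planned. What is at stake is whether the safety tables cover the whole time on drug, including time on a combination that the protocol permits.

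**Working it through.** **1. One patient through the rules.** He has radiographic progression, starts a new therapy outside the three excluded classes on day X, and takes his last dose of study drug on a later day Y.

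| Item | Ends at | Source |
|---|---|---|
| Treatment duration | Y | SAP 7.1, 9.5 |
| Treatment-emergent period | X − 1 day | SAP 7.1 |
| Treatment-emergent period | X | Protocol 10.4 |
| Adverse-event, laboratory and vital-sign summaries | X − 1 day | SAP 9.8.1 to 9.8.3 |

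The time from X to Y is on-drug time that counts as exposure and is absent from the safety summaries.

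**2. How many patients.** No document gives the number who stay on study drug after starting a new therapy, so only a range can be shown.

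- Low anchor: Protocol 3.1 reports that 34 of 1715 treated patients in an earlier enzalutamide trial received study drug together with an antiandrogen or abiraterone after radiographic progression. 34/1715 = 2.0%, and 0.0198 × 1440 = 28.5, about 29 patients. This assumes that the rate carries over. It may be too high, because antiandrogens are in a class that forces discontinuation here. It may be too low, because it counts no other permitted agents.
- Upper limit: SAP 5 expects 360 new-therapy starts at the MFS analysis, 360/1440 = 25%. This includes the three classes that force discontinuation, so it cannot be the expected number.
- The low anchor equals 28.5/360 = 7.9% of starters.

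**3. The plan's own figure.** SAP 5 gives 80% power for time to new antineoplastic therapy (360 events, hazard ratio 0.70, two-sided 0.02, 2:1). Schoenfeld's formula gives √(360 × 2/3 × 1/3) × |ln 0.70| − 2.326 = 8.944 × 0.3567 − 2.326 = 0.864, hence power 80.6%. The figure reproduces.

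**4. What that implies by arm.** With proportional hazards and common follow-up, let p be the placebo proportion starting new therapy:

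960 × [1 − (1 − p)^0.70] + 480 × p = 360

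The solution is p = 30.3% (about 146 of 480). The enzalutamide proportion is 1 − 0.697^0.70 = 22.3% (about 214 of 960). An exponential model with assumed uniform accrual over 24, 30 or 36 months and a cut-off at 43 months gives the same split to within 0.2 points.

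These are starters. The patients affected are starters who stay on study drug. Assuming the same stay-on share in both arms:

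| Assumed share of starters who stay on drug | Placebo | Enzalutamide | Difference (points) |
|---|---|---|---|
| 7.9% (low anchor) | 2.4% | 1.8% | 0.6 |
| 25% | 7.6% | 5.6% | 2.0 |
| 50% | 15.2% | 11.2% | 4.0 |
| 100% (upper limit) | 30.3% | 22.3% | 8.0 |

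If the placebo share were 22.3/30.3 = 0.74 times the enzalutamide share, the difference would be zero. Below that ratio it reverses.

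**5. The collection wording.** Protocol 8.1.4 can be read in two ways. Taken literally, recording stops on day X. Taken as an exception to the preceding sentence, which sets collection to at least 30 days after the last dose, it only shortens the tail after study drug ends. Protocol 5.4.1 and Appendix 5, note 2, use the same idea in that narrower setting. Table 4 fits only the narrower reading. Appendix 5, note 12, follows whichever reading is given to safety follow-up. The text does not settle it, and sites may have differed.

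**The case against.** The strongest reply is that little is truly lost. Later serious events are reported whenever the investigator learns of them (Protocol 8.1.4.1), not only when thought related. Survival status and cause of death are collected throughout (Protocol 9.1.2.1), and overall survival counts every death. Discontinuation reasons are summarised, laboratory values outside the window are still listed (SAP 9.8.2), and Table 4 keeps adverse-event review at every on-treatment visit. Time-adjusted rates truncate events and patient-years alike. All of this is correct. A reader might infer that serious harms vanish from the record, and the documents do not support that. What remains is narrower: none of these routes brings the events into the treatment-emergent, laboratory or vital-sign summaries.

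A reader might also infer that events are lost unequally by arm, because placebo patients should start new therapy more often. That is true of starters under the plan's hazard ratio. No document gives the stay-on share by arm, so neither the size nor, strictly, the direction for affected patients is established.

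A third inference is that the open-label period makes matters worse, since fewer classes are barred there. But its own collection note has no new-therapy stop, patients who will receive other prostate cancer treatment after unblinding are ineligible, and the overlap is not quantified.

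Finally, the double-blind period has ended. Redefining the main tables now would be after the fact, which favours a supplementary summary for data already analysed.

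**Conclusion.** The point holds as a gap in definition. As written, SAP 7.1 and Protocol 10.4 drop on-drug adverse events, laboratory values and vital signs for patients who add a permitted therapy and stay on study drug, while exposure keeps counting. This follows from the text and needs no numerical assumption.

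The size does rest on an assumption. About 29 of 1440 patients is the best anchor if the earlier trial's 2% carries over. The figure of 360 is an upper limit that cannot be reached, because it includes therapies that end study drug. With equal stay-on shares the arms would differ by 0.6 points at the low anchor and at most 8.0 points at the upper limit, but equal shares are assumed, so imbalance is a possibility only. This is a cheap and worthwhile correction. It is not a defect that undermines the safety conclusions.

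**What to change.** 1. In SAP 7.1 and Protocol 10.4, let the treatment-emergent period run to last dose + 30 days, and cut it at a new antineoplastic therapy only when that therapy starts after the last dose of study drug. Use the same day for the cut in both documents.
2. At minimum, keep the present tables and add a supplementary adverse-event, laboratory and vital-sign summary from first dose to last dose + 30 days. For laboratory data this means central values, because the open-label tests are local.
3. In either case, flag events that start after the added therapy, so that they can be shown separately.
4. Reconcile Protocol Table 4, 8.1.4, 8.1.4.1, Appendix 5 note 12 and Supplement Table 1 note 13, so that they state plainly whether adverse-event recording continues while study drug continues.

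The cost is a few sentences and one extra set of tables; Table 4 already schedules adverse-event review at the on-treatment visits. There are two limits. Some added events will be due to the second agent, which the flag makes visible but cannot resolve. Double-blind events that were never recorded cannot be recovered.
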